8.5.1	Investigator reporting: notifying the Dartmouth IRB	18
8.6	UNBLINDING PROCEDURES	189
8.7	STOPPING RULES	189
8.8	MEDICAL MONITORING	199
9	DATA HANDLING AND RECORD KEEPING	20
9.1	CONFIDENTIALITY	20
9.2	SOURCE DOCUMENTS	20
9.3	RECORDS RETENTION	20
10	ETHICAL CONSIDERATIONS	20
11	STUDY FINANCES	21
11.1	FUNDING SOURCE	21
11.2	CONFLICT OF INTEREST	21
11.3	SUBJECT STIPENDS OR PAYMENTS	21
12	REFERENCES	21
13	ATTACHMENTS	23

List of Abbreviations

DLPFC – Dorsolateral Prefrontal Cortex
EEG – Electroencephalogram
EPs – Evoked Potentials
IAPS – International Affective Pictures Set
LF TMS – Low Frequency Transcranial Magnetic Stimulation
MINI - Mini-International Neuropsychiatric Interview
MOCA - Montreal Cognitive Assessment
MT - Motor Threshold
PANAS - Positive and Negative Affect Schedule
QIDS – Quick Inventory of Depressive Symptomatology-Subject Rated and Visual Analog Scale
QOL – Quality of Life
SAFTEE – Systematic Assessment for Treatment Emergent Events
TLE – Temporal Lobe Epilepsy

Study Summary

Title	Safety and Feasibility of Accelerated Low-Frequency Transcranial Magnetic Stimulation for Medication-Resistant Depression in Patients with Epilepsy
Short Title	TMS for Depression in Patients with Epilepsy
Protocol Number	N/A
Phase	Phase 2
Methodology	Non-randomized, non-controlled
Study Duration	11/1/2015 – 10/31/2020
Study Center(s)	DHMC, Lebanon, NH DHMC, Manchester, NH (Recruitment)
Objectives	Primary objective is to determine whether it is safe and feasible to administer low-frequency right frontal lobe transcranial magnetic stimulation using an accelerated protocol to treat depression in patients with focal epilepsy.
Number of Subjects	20
Diagnosis and Main Inclusion Criteria	Epilepsy and moderate symptoms of depression
Study Product, Dose, Route, Regimen	MagVenture transcranial magnetic device with a figure 8 coil, delivered in 15 50-minute trains of 1 Hz; 45,000 total pulses; stimulation intensity between 80-120% of patient's motor threshold
Duration of administration	3 days
Reference therapy	None
Statistical Methodology	

1 Introduction

This document is a protocol for a human research study. This study is to be conducted according to US and international standards of Good Clinical Practice (FDA Title 21 part 312 and International Conference on Harmonization guidelines), applicable government regulations and Institutional research policies and procedures.

1.1 Background

The International League Against Epilepsy defines epilepsy as a disorder of the brain characterized by: (1) an enduring predisposition to generate epileptic seizures; and (2) the neurobiological, cognitive, psychological, and social consequences of this condition[1]. The 2012 Institute of Medicine Report on Epilepsy proposes that treatment of epilepsy should not only focus on seizures, but also on its comorbidities[2]. In response, the National Institute of Neurological Disorders and Stroke (NINDS) established Epilepsy Research Benchmarks, including: Area III: Prevent, limit, and reverse the comorbidities associated with epilepsy and its treatment[3]. Epilepsy comorbidities include several somatic, psychiatric, and cognitive disorders that contribute to the adverse impact of the disease.

The most frequent psychiatric disorder comorbid with epilepsy is depression which is present in approximately 20% of patients[4] and includes patients with both focal epilepsy[5, 6] and idiopathic generalized epilepsy[7, 8]. Patients with epilepsy and depression have significantly decreased quality of life[9] and have increased use of costly medical resources[10]. Despite this, very little research has focused on the effective treatment of depression in epilepsy patients. Critically, about 30% of persons with epilepsy and MDD do not adequately respond to standard pharmacological therapy for treating depression. For patients with medication-resistant depression, there are no quality data to guide treatment.

The manifestations and diagnosis of depression in patients with epilepsy may differ compared to depression occurring in patients without epilepsy. Studies confirm that most frequently depression manifests similarly in patient with epilepsy and without epilepsy fulfilling criteria for DSM major depression disorder [11-13]. However, compared to the general population patient with epilepsy often have more chronic dysthymic course with milder symptoms and fewer fluctuations [14]. Studies show that significant number of patient with epilepsy fail to meet a specific DSM Axis 1 diagnosis for MDD despite self-reporting depression of mild to moderate severity on the Beck Depression Inventory[15].

The etiology of MDD in patients with epilepsy has been controversial with opinions divided between theories of psychosocial versus biological factors. The psychosocial argument highlights the high rates of unemployment, lower rates of educational achievement, lower rates of marriage, higher rates of divorce, relative social isolation, and stigma in patients with focal epilepsy, and temporal lobe epilepsy in particular. In contrast, nearly 30 years of imaging studies have identified numerous abnormalities in brain regions in patients with MDD, including those with focal epilepsy and MDD. Patients with MDD have been shown to have decreased gray matter volume in the frontal lobes, amygdalohippocampal complex and the anterior cingulate[16-18]. Studies in patients with certain types of focal epilepsy and comorbid depression have identified correlations between severity of depression and degree of hypometabolism on PET and cortical thickness on structural MRI in the orbitofrontal cortex, as well as hippocampal and amygdala volume[19-25]. These imaging studies provide strong evidence for a neurobiological basis of depression in patients with focal epilepsies.

In addition to studies using PET and MRI in patients with MDD without epilepsy, investigators have searched for EEG based biomarkers. Higher power in the alpha frequency band defined as 8-12 Hz in the left frontal lobe has been robustly reproduced[26-34]. In addition, theta frequency activity ranging between 4-8 Hz which has been conceptualized as the frequency of communication between cortical areas has been shown to be lower in patients with MDD in the temporal and prefrontal regions and in the cingulate region using dense array EEG techniques[33, 35, 36]. While at Emory, [name] group showed that prefrontal theta power predicted the antidepressant response to deep brain stimulation in patients with highly treatment-refractory depression[37]. Furthermore, more recent studies measuring functional connectivity using dense array EEG source modeling demonstrated elevated coherence between frontal and temporal alpha in MDD[38].

1.2 *Investigational Agent*

Repetitive transcranial magnetic stimulation (TMS) is a nonpharmacological, noninvasive method for stimulating the brain and modulating neural network activity. TMS has shown potential benefit in treating a number of neuropsychiatric disorders, especially depression[39]. With TMS, an electromagnetic coil placed against the scalp is used to generate a rapidly changing, relatively high strength magnetic field (~2 Tesla) that passes unimpeded through scalp and skull and generates an electric current in the underlying cortex. Using current “figure of eight” coils, stimulation can be focused to a 2-3 cm diameter region of cortex, allowing relatively focused stimulation. Due to the rapid decrease in magnetic field strength with distance from the coil, stimulation is generally limited to surface cortical stimulation (e.g., sensorimotor cortices, surface prefrontal cortices). TMS has been investigated as a diagnostic and therapeutic approach for several neuropsychiatric conditions including depression, schizophrenia, obsessive-compulsive disorder, addiction, epilepsy, and parkinsonism.

High-frequency (HF) TMS refers to TMS delivered at a frequency at 5 Hz or above. HF TMS applied to the left dorsolateral prefrontal cortex (DLPFC) is an FDA-approved treatment for medication-resistant depression and is becoming widely available in the community. Left HF DLPFC TMS has established clinically and statistically significant antidepressant effects[40]. However, HF TMS can increase cortical excitability and is associated with an increased risk of seizure[41]. As such, use of FDA-approved depression treatment protocols in patients with epilepsy would be relatively contraindicated, and there has been reluctance to study TMS in patients with epilepsy. Despite this potential increased risk of seizures, at present time the actual risk of a patient with either focal or generalized epilepsy experiencing a seizure during the course of treatment with TMS has not been studied. In addition, there is no evidence to suggest that patient with focal epilepsy or generalized epilepsy differ with regards to the risk of potential seizures by high frequency TMS.

Low-frequency (LF) TMS refers to TMS delivered at a frequency of 1 Hz or below. Unlike HF TMS, LF TMS can decrease cortical excitability and may have anticonvulsant effects[42]. Low frequency TMS applied to right DLPFC also has an extensive though smaller database supporting its antidepressant efficacy, and comparisons to left HF DLPFC TMS suggest both treatments work equally as well[43, 44]. Surprisingly, LF TMS has not been investigated as an antidepressant treatment in patients with epilepsy, though it would have clear advantages compared to HF TMS including increased tolerability and potentially anticonvulsant effects.

The mechanism of action of TMS is not fully known. As HF and LF TMS respectively increase and decrease cortical excitability of the underlying cortex, these local effects likely comprise some of the mechanism. Converging data strongly support a role for the dorsolateral prefrontal cortices in the pathophysiology of depression, and a common abnormal pattern is left-right imbalance in activity characterized by relatively lower left DLPFC activity (e.g., decreased blood flow or metabolism; increased alpha power) and relatively higher right DLPFC activity[30, 45-49]. A simple hypothesis is that TMS works by either “turning up” activity in the left DLPFC versus “turning down” activity in the right DLPFC. One measure of prefrontal cortical activity is alpha power derived from a resting state scalp EEG. Thus, patients with focal epilepsy and comorbid depression would be expected to have left-right asymmetry in prefrontal alpha power. Further, LF TMS to the right DLPFC would be expected to alter prefrontal alpha power asymmetry which may correlate with antidepressant efficacy associated with this intervention. As above, the effects of TMS on prefrontal theta power and prefrontal-temporal alpha coherence may also be involved in the antidepressant mechanisms of TMS.

1.3 *Preclinical Data*

No available non-clinical data is available.

1.4 Clinical Data to Date

Repetitive transcranial magnetic stimulation (TMS) is a non-pharmacological, non-invasive, non-convulsive method for stimulating the brain and modulating neural network activity. High frequency (HF) TMS applied to the left dorsolateral prefrontal cortex (DLPFC) is an evidence-based, FDA-approved antidepressant treatment[39]. However, due to the potential for HF TMS to induce unwanted seizures in susceptible patients (e.g., those with epilepsy), this treatment has never been assessed as a treatment for TRD in patients with epilepsy. Low frequency (LF) TMS of the right DLPFC has also been shown to have antidepressant efficacy and may actually be anticonvulsant; surprisingly, this intervention has never been evaluated as an antidepressant intervention in patients with epilepsy.

1.5 Dose Rationale and Risk/Benefits

Low-frequency (LF) TMS refers to TMS delivered at a frequency of 1 Hz or below. Unlike HF TMS, LF TMS can decrease cortical excitability and may have anticonvulsant effects[42]. Low frequency TMS applied to right DLPFC also has an extensive though smaller database supporting its antidepressant efficacy, and comparisons to left HF DLPFC TMS suggest both treatments work equally as well[43, 44]. Surprisingly, LF TMS has not been investigated as an antidepressant treatment in patients with epilepsy, though it would have clear advantages compared to HF TMS including increased tolerability and potentially anticonvulsant effects.

2 Study Objectives

Specific Aim 1: To examine the safety and feasibility of accelerated low-frequency transcranial magnetic stimulation (TMS) to the right dorsolateral prefrontal cortex in patients with epilepsy and comorbid depression.

Hypothesis 1.a. (safety): Treatment will not produce serious adverse events defined as an increase in seizure rate or hospitalization.

Hypothesis 1.b. (safety): Treatment will not be associated with a higher rate of adverse events as measured by a modified Systematic Assessment for Treatment Emergent Events (SAFTEE) given at baseline and immediately post-TMS.

Hypothesis 1.c. (feasibility): At least 80% of participants will complete the study protocol.

Specific Aim 2: To examine the utility of electrophysiological and behavioral profiles as biomarkers of depression correlated with response to treatment with right-DLPFC TMS in patients with epilepsy.

Hypothesis 2a: Changes in dense array EEG based biomarkers of depression (hemispheric frontal alpha power asymmetry, anterior cingulate theta power, and frontotemporal alpha coherence) will correlate with changes in depression scores.

3 Study Design

3.1 General Design

This protocol is for a pilot study designed primarily to assess whether patients with epilepsy can safely tolerate low-frequency transcranial magnetic stimulation in an accelerated protocol to treat depression. We aim to enroll 20 patients with epilepsy and comorbid depression to receive a total of 14 hours of transcranial magnetic stimulation over 3 days at DHMC - Lebanon. We will assess safety of this protocol with regards to seizure frequency and other side effects of TMS treatment and the feasibility of using an accelerated protocol in this patient population. In addition to these primary aims, our secondary goal is to determine if dense array EEG can provide a useful biomarker for depression and its treatment in epilepsy. We will obtain a structural MRI before treatment and a dense array EEG before and after TMS treatment to assess for changes in specific dense array EEG based biomarkers. We will obtain a function MRI before treatment, and a dense array EEG before and after TMS treatment. Subjects will complete a brief battery of neuropsychological testing

before and after the treatment to assess for any changes in social cognition or executive functioning that may result from TMS or the change in depressive symptoms.

In addition to recruiting patients, we will likewise recruit family members or friends of the patient and ask them to monitor the patient for side effects to TMS treatment. The recruited family member will bring the patient to the treatment and stay with the patient overnight at a local hotel and monitor for possible seizures or other adverse events of treatment. Family members will be instructed in seizure safety and be given emergency phone numbers to call if the patient is experiencing adverse effects of TMS. When feasible, patients and their family members will be given the option to commute to the medical center on treatment days rather than staying in a local hotel.

3.2 Primary Study Endpoints

1. Change in weekly seizure rate as assessed by self-report seizure log.
2. Change in significant side effects as assessed by the Systematic Assessment for Treatment Emergent Events (SAFTEE)[50].
3. Feasibility of participation such that 80% of patients will complete the study protocol including all measures, MRI, dense array EEG, and TMS.
4. Correlation of pre and post TMS hemispheric frontal alpha power asymmetry, anterior cingulate theta power, and frontotemporal alpha coherence with changes in depression severity.

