6.1 Visit 1a: Initial Screening by Neurologist – Pre-enrollment

- Patient will review and sign informed consent.
- Initial screening will be done by a board-certified neurologist (, Visit 1a). Patient's history and physical will be taken, medications will be reviewed, seizure log, MOCA will be performed if time permits. All incomplete assessments may be done at Visit 1b.
- Subject will receive seizure log and instructions for its use.

6.2 *Visit 1b: Initial Screening by Psychiatrist – Pre-enrollment*

- Subsequent evaluation will be done by board-certified psychiatrist and research assistant Visit 1b). If the subject is unable to complete the full screening during Visit 1a, he or she may be scheduled for a second screening appointment with study psychiatrist and research assistant. At that time, diagnosis of medication-resistant depression will be confirmed; the MINI, QIDS, SAFTEE, PANAS MRI safety, TASS and ATHF will be performed. Seizure log data will be obtained.
- If time permits, Visit 2 procedures can be done at Visit 1b.

6.3 *Visit 2: Imaging and Baseline Neuropsychological Testing – Pre Enrollment*

- Patient will be report to the Advanced Imaging Center for MRI. MRI will last approximately one hour.
- After MRI is complete, patient will be brought to the EEG lab . A dense-array EEG will be conducted which will take approximately one hour.
- Patient will do neuropsychological and social-cognition testing, which will last approximately 2 hours. (QOLIE-31, RBANS and MAC-S)
- If time permits, TMS motor threshold may be done at Visit 2, so long as TMS treatment is scheduled to begin within one week. Otherwise, TMS motor threshold will be done at Visit 3.

6.4 *Visit 3: Enrollment and first day of TMS treatment*

- Patient will be brought to DHMC by their proxy for the first day of TMS treatment.
- Research staff will administer the QIDS, SAFTEE, and PANAS. Data will be obtained from the patient's seizure log.

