7.3 Subject Population(s) for Analysis

The patients successfully initiating the trial will be the analysis population to the safety outcomes. The patients completing the TMS will be the population for the secondary outcomes.

8 Safety and Adverse Events

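### The 80% completion endpoint has no defined denominator; if it is the 20 enrolled patients, losses at the pre-enrollment MRI, EEG and testing visit are not counted and completion is overstated

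*Combined protocol and SAP*

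**What the plan says.** Hypothesis 1.c (Section 2) sets the target: "At least 80% of participants will complete the study protocol". Section 3.2 spells out what completion covers: "80% of patients will complete the study protocol including all measures, MRI, dense array EEG, and TMS". Section 7.1 compares the completion rate with 80% by an exact binomial test, without naming the patients over whom the rate is taken.

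The visit schedule in Section 6 runs as follows.

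- Visit 1a (6.1): "Patient will review and sign informed consent".
- Visit 1b (6.2): the psychiatrist's screening, which settles final eligibility according to Section 4.2. Visit 2 procedures may be brought forward to this visit.
- Visit 2 (6.3), headed "Visit 2: Imaging and Baseline Neuropsychological Testing – Pre Enrollment": MRI, dense-array EEG, and about two hours of testing.
- "Visit 3: Enrollment and first day of TMS treatment" (6.4).

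On numbers, Section 3.1 says "We aim to enroll 20 patients with epilepsy and comorbid depression". Section 5.2 places all 20 in the treatment group on enrollment and expects MRI and EEG in every patient. Section 8.7 equates more than four drop-outs with failure of the 80% feasibility target. Section 7.3 defines populations for the safety outcomes and the secondary outcomes only.

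**The concern.** Part of what the endpoint counts as completion is over before the point that the protocol calls enrollment. No visit after Visit 2 includes a scan, so the MRI component can fail only before enrollment. If the rate is taken over enrolled patients, a patient who cannot tolerate the scanner or the electrode net, or does not finish the testing, and therefore never reaches Visit 3, appears in neither numerator nor denominator.

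Such a patient is not a screen failure in the usual sense. Consent has been given, final eligibility is settled at the psychiatrist's visit, and Section 4.1 judges MRI eligibility on a safety form rather than on a finished scan. This is a failure of the kind that Section 3.2 sets out to measure.

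Feasibility is a primary aim. With about 20 patients, one to three people can move the rate across the target. An undefined denominator also lets the base be chosen once the results are known.

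**Working it through.** **Inputs.** Target 0.80 (Sections 2, 3.2, 7.1); 20 patients to be enrolled (3.1, 5.2); more than four drop-outs equated with the 80% target (8.7). The number of consented, eligible patients lost at Visit 2, k, is not given and is an assumption here, shown over a range that includes zero.

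**Step 1: the plan's own figure.** (20 − 4)/20 = 16/20 = 0.80. The 80% in Section 8.7 reproduces on a base of 20. It fits a denominator of the 20 enrolled but does not prove it, because Section 8.7 does not say from which visit drop-outs are counted.

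**Step 2: add the Visit 2 losses.** Suppose that 20 patients are enrolled, x of them complete everything, and k further eligible patients are lost at Visit 2 and never enrolled. The rate over enrolled patients is x/20; the rate over eligible patients is x/(20 + k).

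| x of 20 enrolled | k = 0 | k = 1 | k = 2 | k = 3 | k = 4 |
|---|---|---|---|---|---|
| 16 | 80.0% | 76.2% | 72.7% | 69.6% | 66.7% |
| 18 | 90.0% | 85.7% | 81.8% | 78.3% | 75.0% |
| 20 | 100% | 95.2% | 90.9% | 87.0% | 83.3% |

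The enrolled-patient rate exceeds the eligible-patient rate by the factor (20 + k)/20: 1.05 at k = 1, 1.10 at k = 2 and 1.20 at k = 4.

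**Step 3: when the target is crossed.** x/(20 + k) < 0.80 requires k > 1.25x − 20. At x = 16 this is k > 0, so one loss is enough. At x = 18 it is k > 2.5, so three are needed. At x = 20 it is k > 5, so six are needed (20/26 = 76.9%).

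**Step 4: the exact test.** Section 7.1 gives neither sidedness nor level; one-sided 5% is assumed for illustration. With 20 patients, P(X = 20 | 0.80) = 0.8^20 = 0.0115 and P(X ≥ 19) = 0.069, so only 20/20 shows a rate above 80%. With one Visit 2 loss in the denominator, 20/21 gives 0.8^21 + 21 × 0.2 × 0.8^20 = 0.0092 + 0.0484 = 0.058. A single loss takes away the only significant result.

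**Step 5: the same effect as a proportion.** Let c be completion among the enrolled and q the share of eligible patients lost at Visit 2 (assumed 5% to 20%). Completion from eligibility is c(1 − q). For c = 0.90 this is 0.855, 0.81 and 0.72 at q = 5%, 10% and 20%. The chance of seeing at least 16 of 20 is 95.7% when the 20 are counted from enrollment. When they are counted from confirmed eligibility it is 84.7%, 67.3% and 30.2%.

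**The case against.** A reader might infer that the plan removes Visit 2 failures from the denominator, so that reported completion is bound to be too high. The documents do not support that.

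- The denominator is undefined. Sections 2 and 3.2 speak only of participants and patients. Consent at Visit 1a would allow a count that keeps Visit 2 losses, and Section 4.1 attaches the figure of 20 to recruitment on the initial criteria, a step before the psychiatrist's screening.
- Section 7.3 does not settle it. Its sentence, "The patients successfully initiating the trial will be the analysis population to the safety outcomes", is confined to safety.
- A finished MRI, EEG or test battery is not a written condition of enrollment. A patient who stops the scan could start TMS at Visit 3 and be counted as a non-completer. Near-complete MRI and baseline EEG by construction is therefore not established.
- Most of the endpoint can still fail after enrollment: the TMS course, the EEGs at Visits 5, 7 and 9, testing at Visits 7 and 9, and the scales to six months.
- Section 3.1 ties feasibility to the accelerated protocol, for which patients starting TMS are a defensible base.
- The visit guide, procedures table and monitoring plan listed in Section 13 are not in the text reviewed and may bear on this.

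All of this stands, and it makes the overstatement conditional. It does not remove the gap: a primary endpoint is tested against a fixed target with no stated denominator, and the passages that give a number lean towards the base that leaves out Visit 2 losses.

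**Conclusion.** The point holds in conditional form. What is certain is that the completion denominator is undefined, and that the MRI and the baseline EEG and testing count towards completion while preceding enrollment. Completion is overstated if two things are true: the base is enrolled patients, and at least one eligible patient is lost at Visit 2 without being enrolled. The figures also assume that enrollment continues until 20 have started; no replacement rule is written.

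Under those assumptions the overstatement is about 4 percentage points per loss near the target for the first few losses. That is enough to bring 16/20 below 80% with one loss, and 18/20 below it with three. The bias is confined to the MRI and baseline components. With no Visit 2 losses there is none.

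**What to change.** In Sections 3.2, 7.1 and 7.3:

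- Define the feasibility population as all patients who consented and were confirmed eligible at the psychiatrist's screening, and use it in the exact test.
- Count a patient who does not complete the MRI, baseline EEG or baseline testing as a non-completer, including when these are done at Visit 1b, so that the rule follows the procedure and not the visit label.
- Report completion among patients starting TMS as a second figure. This keeps the question about the accelerated course visible and shows where losses occur.

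In Section 8.7, state which base the equation of more than four drop-outs with 80% refers to, and whether a Visit 2 loss is a drop-out. On a base of 20 + k the equation no longer holds as written, so the passages must be reconciled.

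The cost is wording and a participant-flow count from consent onwards; no visit or procedure changes. The completion figure may be slightly less favourable, and its denominator is no longer a number fixed in advance.
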